8.3.6 Follow up visits (Visit 6 and 7)

Visits 6 [15 (+/- 5 Days)] and 7 [29(+/-7)] have no treatment component. There will be at least 2 days between Visit 5 and 6 and 3 days between Visits 6 and 7.

Assessments at Visit 6 and 7 are:

- Review of any medication changes
- Completion of HDRS questionnaire
- Completion of YMRS questionnaire
- Completion by participant of the POMS questionnaire (optional)
- Completion of CGI-S
- Completion of CGI-I
- Completion by participant of CANTAB subscales (Visit 6) (optional)
- Completion of MADRS questionnaire
- Completion of GAF questionnaire
- Completion of WAIS (optional)
- Completion of NEOPI-FFI (optional)
- Adverse event assessment (see section 10.1)
- Participant assessment of treatment group (IV Scopolamine or IV Saline) (Visit 7)

Visits 6 and 7 maybe conducted over the telephone if necessary but only in limited circumstance such as participant withdrawn or unwilling /unable to attend clinic for scheduled visit.

An outline of scheduled study assessments and procedures are outlined below in table 2.

Table 2: Schedule of Assessments

Procedures	Visit 1 Screening	Visit 2			Visit 3			Visit 4			Visit 5			Visit 6 Day 15 (± 5 Days) Follow-Up	Visit 7 Day 29 (± 7 Days) Follow-Up		
		PLACEBO			Randomisation Day 0 Scopolamine or Placebo			Day 4 (± 2 Days) Scopolamine or Placebo			Day 8 (± 2 Days) Scopolamine or Placebo						
		IV Infusion			IV Infusion			IV Infusion			IV Infusion						
		Pre	During	Post	Pre	During	Post	Pre	During	Post	Pre	During	Post				
Signed informed consent	X																
Inclusion/Exclusion	X	X			X***												
Randomisation					X												
IWRS					X			X			X						
Demography	X																
MEHI	X																
Medical/Surgical History/History BPD	X																
Current Medication	X	X			X			X			X			X	X		
Vital Signs – HR, BP & RR	X	X		X	X		X	X		X	X		X				
SCID-RV	X																
HDRS	X	X			X			X			X			X	X		
YMRS	X	X			X			X			X			X	X		
AUDIT	X																
Pregnancy Discussion	X	X			X			X			X						
Contraception Advice	X	X			X			X			X						
Serum Pregnancy Test ^A	X																
Pregnancy urine dipstick ^A	X				X			X			X						
U&Es, LFTs, TFTs °	X	X															
Fagerstrom	X																
CGI-S		X			X			X			X			X	X		
CGI-I					X			X			X			X	X		
VAS		X		X	X		X	X		X	X		X				
MADRS		X			X			X			X			X	X		
GAF					X						X			X	X		
ECG		X															
Height (cm) & Weight (kg)		X									X						
IV Cannulation		X			X			X			X						

Procedures	Visit 1 Screening	Visit 2			Visit 3			Visit 4			Visit 5			Visit 6 Day 15 (± 5 Days) Follow-Up	Visit 7 Day 29 (± 7 Days) Follow-Up		
		PLACEBO			Randomisation Day 0 Scopolamine or Placebo			Day 4 (± 2 Days) Scopolamine or Placebo			Day 8 (± 2 Days) Scopolamine or Placebo						
		IV Infusion	IV Infusion	IV Infusion	Pre	During	Post	Pre	During	Post	Pre	During	Post				
Infusion administration		X				X			X			X					
Adverse Events		X	X	X	X	X	X	X	X	X	X	X	X	X	X		
Cannulation Site Check		X		X	X		X	X		X	X		X				
POMS (Optional)		X		X	X		X	X		X	X		X		X		
CANTAB ** (Optional)			X			X								X			
WAIS * (Optional)			X*			X*			X*			X*	X*	X*	X*		
NEO-PI-FFI * (Optional)			X*			X*			X*			X*	X*	X*	X*		
PRISE (Optional)			X			X			X			X					
Subjective Assessment															X		

Randomisation will only occur at Visit 3 after HDRS is demonstrated to be ≥ 8 and YMRS < 6 . These measures will be conducted pre-randomisation (and consequently also pre-infusion).

Pre-infusion vital signs should be taken post cannulation. Post-infusion vital signs within 15 minutes of infusion stopping and 50 to 90 minutes post-infusion.

Visit 6 and 7 can be conducted by telephone in limited circumstances if a participant has withdrawn or is unwilling/unable to attend clinic at the scheduled time.

* Can be undertaken at any of the marked visit

** These include Paired Associates Learning (PAL), Spatial recognition, Delayed Match to Sample, ID-ED Shift, motor screening and Eyes of the Mind tests.

***Only inclusion criterion 7 and exclusion criteria 21 and 22 are required to be met for randomisation at Visit 3 only

Δ Pregnancy test (serum pregnancy test and pregnancy urine dipstick), when required, for female participants only. Serum result confirmed prior to Visit 3.

◦ Blood tests for U&Es (Urine and Electrolytes), LFTs (Liver Function Tests) and TFTs (Thyroid Function Tests) should be confirmed within acceptable ranges in the previous 4 months of the Screening (Visit 1). Can be performed if required at Visit 1 or 2 (results must be confirmed as acceptable prior to infusion).

AUDIT = Alcohol Use Disorder Identification Test; **BP** = Blood Pressure; **CANTAB** = Cambridge Neuropsychological Test Automated Battery, **CGI-I** = Clinical Global Impression – Improvement, **CGI-S** = Clinical Global Impression- Severity, **ECG**= Electrocardiograph; **Fagerstrom**: Test for Nicotine Dependence, **GAF** = Global Assessment of Functioning; **HDRS** = Hamilton Depression Rating Scale; **HR** = Heart Rate; **IV** = Intravenous; **IWRS** = Interactive Web Response System; **MADRS** = Montgomery and Asberg Depression Rating Scale; **MEHI** = Modified Edinburgh Handedness Inventory; **NEO PI-FFI** = NEO Personality Inventory-Five Factor Inventory; **POMS** = Profile of Mood States; **PRISE**= Patient Rated Inventory of Side Effects; **RR** = Respiratory Rate; **SCID-RV** = Structured Clinical Interview for DSM; **VAS** = Visual Analogue Scale; **YMRS** = Young Mania Rating Scale; **WAIS** = Wechsler Adult Intelligence Scale.

Note timeline between visits:

Visit 1 and 2: ≤ 14 days. Can also occur on the same day and thus data from screening visit does not need to be replicated at Visit 2.

Visit 2 and 3: ≥ 2 days and ≤ 7 days

Visit 3 and Visit 4 and Visit 5 and Visit 6: ≥ 2 days

Visit 6 and Visit 7: ≥ 3 days

8.4 Description of Study Procedures

8.4.1 Informed Consent

Eligible participants may only be included in the trial after providing written informed consent. Informed consent must be obtained prior to conducting any trial specific procedures and the process for obtaining informed consent must be fully documented in the patient's medical records.

The central ethics committee (EC) approved Patient Information Leaflet and Informed Consent Form (PIL and ICF) will be provided to potential participants, which the member of the research team, Principal Investigator and/or Sub Investigator's will explain and discuss the nature of the study. Potential participants will have ample time to ask and have answered any questions prior to making a decision regarding participation.

When the participant is ready to do so, the ICF will be initialled, signed and dated by the participant, and the Principal Investigator and/or Sub-Investigators who administered the informed consent form. The complete original ICF will be filed by the site in the site file, a copy of the ICF will be given to the participant and a copy will be filed in the participant's notes.

8.4.2 Medical and Surgical History

Details of current and previous relevant diagnoses and treatments will be recorded as deemed relevant by PI / Sub PI or research team. In particular, medical history of cardiovascular disease, prostatic hypertrophy, asthma, hepatic or renal impairment, gastrointestinal obstruction, epilepsy and thyrotoxicosis should be sought.

8.4.3 Demographics

The date of birth, gender, race and handedness will be recorded. Handedness will be accurately measured utilising the Modified Edinburgh Handedness Inventory (MEHI, Oldfield, 1971; Tan, 1988).

8.4.4 Physical Examination

Height (cm) and weight (kg) will be recorded at Visit 2. The weight at Visit 2 will be used for the duration of the study to inform dose calculations.

8.4.4.1 Vital signs

Vital signs will be recorded for all participants and will include: blood pressure (BP), heart rate (HR) (beats per minute (bpm)), and respiratory rate (RR) (respirations per minute). These will be recorded at screening, Visit 2 and at Visits 3, 4 and 5. Patients will rest for 5 minutes before measurements are obtained. Vital signs will be recorded prior to infusions and post infusions. Prior to infusion vital signs should be obtained post cannulation.

For post infusion vital signs will be taken within 15 minutes post-infusion administration and fifty to 90 minutes post-infusion, resting HR and BP will be measured, with a requirement for a HR ≥ 50 bpm, and BP ≥ 90 mm Hg Systolic and ≥ 60 mm Hg diastolic prior to visit completion. Clinical support is present to support and advise research staff and participants in relation to the management or treatment strategies that are required if the participants HR is < 50 bpm

or > 100bpm or if participant is hypotensive (BP < 90/60). Clinical support includes ready access to resuscitation equipment and clinical expertise.

Where BP and / or HR are abnormal when measured post-infusion the participants respiratory rate will additionally be recorded, and this information will be provided to an on-site clinician.

All participants will be required to remain in the HRB-CRFG for a period of observation by trial staff for a minimum of 90 minutes post infusion. Participants should be asymptomatic of potential IMP related symptoms as well as having satisfactory vital signs before discharge post infusion.

8.4.4.2 ECG Test

An ECG will be performed at Visit 2. Abnormal findings will be noted for clinical significance and the report will be signed by the investigator. If deemed required by the treating physician, additional input will be obtained by an additional registered medical practitioner prior to continuation in the study.

8.4.5 Laboratory Tests

Prior to engagement in the clinical study, trial participants will demonstrate no renal/hepatic impairment and no evidence of thyrotoxicosis. This will be based on an evaluation of medical history and blood tests including Urea and Electrolytes (U&Es), Liver Function Tests (LFTs) and Thyroid Function Tests (TFTs). The most recent U&Es, LFTs and TFTs baseline must be demonstrated to be within acceptable range in the previous 4 months of the Screening visit (visit 1). If no blood tests have been completed within the last 4 months, these will be performed at Visit 1 or Visit 2 and confirmed as acceptable prior to first infusion. Where results are obtained that are outside the laboratory stated normal range, this will be discussed with the PI and where required, the PI will further liaise with clinical colleagues to ensure that any findings are not clinically significant and are acceptable prior to administration of IMP or placebo. If clinically significant, in the opinion of the investigator, the participant will not receive IMP or placebo.

Women of child-bearing potential must have a negative pregnancy test. A urine pregnancy dipstick test will confirm pregnancy status at Visits 2, 3, 4 and 5 prior to each infusion. A serum pregnancy blood test will additionally be conducted at Visit 2 and this will confirm pregnancy status prior to infusion at Visit 3 (placebo/Scopolamine).

8.4.6 Current Medications

All medications will be recorded and changes in psychotropic medication recorded at each study visit. All over-the-counter or prescription medication, vitamins, and/or herbal supplements will be recorded in the patients notes. The indication for treatments will be recorded. Psychotropic medications prescribed over the previous 6 months will additionally be recorded.

8.4.7 Pregnancy and contraception Advice

Women of childbearing potential can only be included in the study if they have a negative urine dipstick test at Visits 2, 3, 4, 5 prior to infusions and a negative blood serum pregnancy test executed at Visit 2 and confirmed prior to infusion at Visit 3.

Women of child-bearing potential are defined as all women physiologically capable of becoming pregnant, unless they are using highly effective methods of contraception during dosing of study treatment (Visits 1-5). Highly effective contraception methods include:

- Female sterilization (have had surgical bilateral oophorectomy with or without hysterectomy) or tubal ligation at least six weeks before taking study treatment.
- Male partner sterilization
- Combination of any two of the following (advice will be provided to all appropriate female participants):
 - a. Barrier methods of contraception e.g. Condom
 - b. Use of oral, injected or implanted hormonal methods of contraception or other forms of hormonal contraception
 - c. Placement of an intrauterine device (IUD) or intrauterine system (IUS)
- Women who are considered post-menopausal i.e. amenorrhea at least 12 months or undergone hysterectomy/bilateral oophorectomy
- All males participating in this study should similarly be provided with adequate contraception advice as detailed above.

8.5 Psychometric Instruments

The timings of administration of the below questionnaires is provided in Table 2. The SCID-RV, HDRS, YMRS, MADRS, GAF, AUDIT, Fagerstrom and VAS should be completed on all participants. The other listed psychometric instruments are desirable but not compulsory and are indicated as optional (POMS, CANTAB, PRISE, WAIS, NEO-PI-FFI). The POMS and VAS should be completed a minimum of 15 minutes post-infusion. The WAIS and NEO-PI-FFI can be completed at any of the scheduled visits. Details of each psychometric instrument is provided below:

- Alcohol Use Disorder Identification Test (AUDIT, Babor et al., 2001). A 10-item questionnaire to identify harmful use or dependence on alcohol.
- The Cambridge Neuropsychological Test Automated Battery (CANTAB; Owen et al., 1995; Sahakian et al., 1988) will be undertaken with participants. Tests conducted from this battery will entail the Paired Associates Learning, Spatial recognition, ID-ED shift, delayed match to sample, motor screening and eyes to mind test. These tests will be used to evaluate visual, new and spatial memory, motor speed and social cognition.
- Clinical Global Impression (CGI, Guy, 1976). A rating scale that measures illness severity (CGI-S) (1-7), and global improvement (CGI-I) (1-7) and has an efficacy index (which relates therapeutic effect to adverse effects) (1-4).
- Fagerstrom Test for Nicotine Dependence (Heatherton et al., 1991). A 6-item questionnaire examining nicotine dependence.
- Global Assessment of Functioning (GAF, Hall, 1995). A rating scale from 1-100 that measures an individuals' functioning and is observer rated.
- Hamilton Depression Rating Scale (HDRS, Hamilton, 1960). A 21-item observer rated instrument that measures symptoms of depression.
- Montgomery and Asberg Depression Rating Scale (MADRS, Montgomery & Asberg, 1979). A 10-item observer rated scale that measures symptoms of depression.
- NEO Personality Inventory-Five Factor Inventory (NEO PI-FFI, Costa & McCrae, 1992). This 60 item personality inventory measures personality traits in five dimensions (neuroticism, extraversion, openness to experience, agreeableness and conscientiousness).
- Patient Rated Inventory of Side Effects (PRISE). A 9 item self-report instrument measuring adverse effects associated with the gastrointestinal, genitourinary, nervous,

cardiac systems, sense organs, skin, sexual functioning, sleep and other general adverse effects.

- Profile of Mood State (POMS, McNair et al., 1971). A rating scale where 65 adjectives are rated by participants on a 5-point Likert scale. Six factors are derived from these adjectives (tension, depression, anger, fatigue, vigour and confusion).
- Structured Clinical Interview for DSM-V Axis I Disorders (SCID-RV, First et al., 2015). This is a semi-structured interview that evaluates pathology and has a demographic section followed by nine diagnostic modules, including two that examine mood disorders.
- Visual Analog Scale (VAS). A series of scales will be created to indicate on a 10-point Likert how participants feel they are on the following items (happy, restless, sad, anxious, anger, drowsiness and alertness). These items are consistent with that used by Furey et al. (2012) in their study of Scopolamine in mood disorders.
- Wechsler Adult Intelligence Scale (WAIS, Wechsler, 1955) is a structured instrument to estimate IQ.
- Young Mania Rating Scale (YMRS, Young et al., 1978). An 11-item observer rated instrument that measures symptoms of mania.

8.6 Randomisation

Participants will be randomly assigned to receive either scopolamine or placebo in a 1:1 ratio. Randomly permuted blocks of sizes 4 and 6 will be used to ensure similar numbers of participants in each arm of the trial.

Randomisation will be stratified by the HDRS score at trial entry (a score of <23 indicating a mild-moderate depressive episode and a score ≥ 23 indicating a severe depressive episode) to ensure greater balance between arms in the final trial sample and increase the efficiency of our treatment effect estimates.

A validated randomisation system will be used at Visit 3, (after HDRS and YMRS are completed) to randomise patients to either arm. This centralised system will ensure allocation concealment; preventing blinded trial staff from knowing which treatment group will be allocated. Blocks of randomly varying length will also reduce the predictability of the allocation sequence.

8.7 Discontinuing/Stopping Infusions

If a trial participant requires medical intervention during or post infusion, the treating physician must assess if it is appropriate to proceed with the current and/or future infusions. If infusions are not completed participants would be asked to complete all other aspects of scheduled visits.

8.8 Blinding

This trial will be conducted in a double-blind fashion with placebo control identical to Scopolamine solution to avoid bias in the assessment of outcomes.

Site Investigators, site personnel, participants, and outcome assessors will be blinded to treatment allocation. Placebo infusion must be prepared, labelled and administered to match procedures for Scopolamine (hyoscine hydrobromide) infusion in order to maintain the blind. Placebo and Scopolamine are identical, colourless solutions and infusions are identical once prepared. Blinding will be maintained as per the process steps and controls outlined in the study specific Investigational Medicinal Product (IMP) Handling Manual. The unblinded study member will be unblinded throughout the length of the study and will not be involved in any

patient assessments or data analysis. Study personnel who administer the infusions to the participants must remain blinded. Discussions regarding treatments between the unblinded team member and the blinded team member must be avoided where possible.

Unblinding will be as per the instructions outlined in the study specific procedure provided to site by the sponsor. Unblinding for one or all participants will take place if it is in the best interests of the participants. In the case of an emergency, when knowledge of the treatment assignment is essential for the clinical management of the participant, a caring physician may unblind a single participant. Any breaking of the blind, whether intentional or unintentional will be recorded and reported to the sponsor as soon as possible. Unblinding will be recorded and justified in the final report.

Circumstances in which unblinding for multiple or all participants may take place include SUSARs, reporting for multiple SAEs or SARs, or if there is new information regarding the safety of the IMP as determined by the caring physician.

8.9 Definition of end-of-trial

The end of trial will be the date of the last visit of the last participant (50th randomised participant). The Sponsor, the funder (Stanley Medical Research Institute (SMRI) and/or Data safety and monitoring board (DSMB) /Trial steering committee (TSC) have the right at any time to terminate the study for clinical or administrative reasons. The end of the study will be reported to the approving EC and HPRA within 90 days of the end of the clinical trial, or within 15 days if the study is terminated prematurely by the Sponsor or the Sponsors representative. The EU Declaration of the End of Trial form must be used for this. The investigators will inform participants and ensure that the appropriate follow-up is arranged for all involved. A summary report of the study will be provided to the REC and HPRA within 1 year of the end of the study.

8.10 Premature termination of the study

The trial may be terminated prematurely if:

- new information about safety or efficacy becomes available
- there is unsatisfactory progress of the study, including unsatisfactory progress in relation to participant recruitment.
- if deemed necessary by the Sponsor, Chief investigator, DSMB, TSC, and / or SMRI

If the trial ends prematurely then the HPRA and the approving EC will need to be informed as required.

8.11 Discontinuation/withdrawal of participants from study protocol

Study participants have the right to voluntarily discontinue study treatment or withdraw from the study at any time for any reason without any consequences.

The investigator has the right to discontinue a participant from study treatment or withdraw a participant from the study at any time if it is in the best interest of the participant. In this instance, participants must discontinue the investigational medicinal product (Scopolamine) and be withdrawn from the study. Reasons for investigator to discontinue a participant from study treatment include but are not limited to:

- Pregnancy,
- Involuntary detention under the MHA 2001 in an acute psychiatric inpatient unit
- Treatment with ECT
- Severity of symptoms such that participation in a clinical trial is not appropriate because of the risk of imminent self-harm (based on review by clinician at study visit)
- Development in the study of narrow angle glaucoma, myasthenia gravis, paralytic ileus, pyloric stenosis, toxic megacolon and acute porphyria.
- Development post-infusion of bradycardia (HR < 50 bpm), tachycardia (HR > 100bpm) or hypotension (Systolic BP <90mm HG or Diastolic BP <60mm Hg) that required clinical treatment (e.g. administration of additional medications, review in Emergency Department)
- Treatment at day of infusion with anticholinergic medications (e.g. Physostigmine, Biperiden, Procyclidine)

If a participant withdraws before completing the study, the reason for withdrawal must be documented in their medical notes. Participants who request to have no further infusions, will be invited to complete pre-infusion questionnaires for remaining treatment visits. Ideally, all participants who discontinue the study should comply with specified follow-up procedures (days 15 +/-5, days 29 +/-7) as detailed in this protocol (i.e. assessments via interview compromising psychometric instruments, discussion of adverse effects and medication and phlebotomy – Table 2, Section 8.3). If the participant is unable to attend for follow-up procedures, a telephone interview will be offered to attain relevant study data. The only exception to this requirement is when a participant withdraws consent for all study procedures. If a study participant withdraws consent after just receiving or during an infusion, monitoring for 50-90 minutes post infusion for bradycardia, hypotension, dizziness and sedation must occur, with the study specific Adverse Event Form completed.

If a participant withdraws due to an adverse event, the investigator will arrange for follow-up visits until the adverse event has resolved or stabilised.

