9.8.2 Prohibited medications

The following medications are contraindicated during the randomised treatment period as they may potentially alter the pharmacokinetics of Scopolamine and any participants newly prescribed these medications at randomisation visit will be excluded from the trial prior to any infusion being administered.

- Physostigmine
- Biperiden
- Procyclidine
- Tricyclic Antidepressants with significant anticholinergic properties (e.g. Amitriptyline and Nortriptyline) that are causing the participant to experience anticholinergic side effects (e.g. blurred vision, constipation, urinary retention, cognitive difficulties).

Participants prescribed any of the above agents during the trial will not receive any further intervention (infusions of Scopolamine or placebo), however will be followed up for the remainder of the trial with data collected included in intention-to-treat analyses if one infusion and one follow-up assessment have been completed.

Participants cannot participate in any other IMP studies while participating in this study (Visits 2-7).

10. Safety reporting

Adverse events will be captured for all study participants from the time of consent for the duration of their participation in the study i.e. from the time of consent to their final study visit. A full AE review at each study visit will ensure that a complete evaluation of the safety and tolerability of the IMP is conducted.

All participants will have their heart rate and blood pressure measured prior to infusion and post-infusion to measure haemodynamic changes, with normal results (see section 8.4.4.1) required post-infusion prior to the participant completing their visit (minimum 90 min monitoring period).

If the readings have not returned to normal within this required 90-minute monitoring period a further period of monitoring will be conducted. A treating investigator must assess and decide if medical intervention is required based on their clinical judgement. Additionally, the PRISE questionnaire (this is optional for participants) will be used where participants agree to document other adverse effects prior to participants completing their clinical visits 2, 3, 4, and 5 (see Section 8.5). All adverse events will be reported to the Sponsor on the AE case report.

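### Protocol 8.11 can be read as withdrawing from the study anyone the investigator discontinues; this conflicts with 8.7, 9.8.2 and its own follow-up text, and puts Visit 6 HDRS at risk

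*Protocol*

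**What the plan says.** Protocol 8.11 opens its investigator paragraph with two separate options: "The investigator has the right to discontinue a participant from study treatment or withdraw a participant from the study at any time". The next sentence merges them: "participants must discontinue the investigational medicinal product (Scopolamine) and be withdrawn from the study". The list of seven reasons that follows is headed only as grounds for stopping treatment: "Reasons for investigator to discontinue a participant from study treatment include but are not limited to".

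Other places give a different rule once infusions stop:

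- Protocol 8.7, on medical intervention during or after an infusion: "If infusions are not completed participants would be asked to complete all other aspects of scheduled visits".
- Protocol 9.8.2, on participants prescribed the listed anticholinergics during the trial: no more infusions, "however will be followed up for the remainder of the trial with data collected included in intention-to-treat analyses", provided that one infusion and one follow-up assessment were completed.
- Protocol 8.11, further down: "Ideally, all participants who discontinue the study should comply with specified follow-up procedures". It adds the offer of a telephone interview, then calls this a requirement with a single exception, withdrawal of consent for all study procedures.
- Protocol 8.3.6 permits Visits 6 and 7 by telephone in limited circumstances and gives a withdrawn participant as an example.
- Protocol 10.3.1 requires an end-of-study assessment when a participant leaves treatment because of an adverse event, without tying it to Visit 6.
- SAP 14.4 says that participants who become pregnant are discontinued from the study, not only from treatment.

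Protocol 11.3 and SAP 9 analyse all randomised participants with available follow-up data. Protocol 11.5.1 and 11.8 and SAP 10.2 and 13.1 derive the missing-data weights from pre-randomisation measurements.

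**The concern.** An intention-to-treat comparison needs the Visit 6 HDRS of people who stopped infusions. A site that follows the mandatory sentence in 8.11 literally could stop collecting it.

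The loss would not be random. Three of the seven listed reasons (involuntary detention, ECT, imminent self-harm risk) reflect severe psychiatric state, so missingness would track the outcome. A fourth, a treated heart-rate or blood-pressure event, may fall unevenly between arms, because Protocol 17.4.1.4 reports transient falls in both with scopolamine. The two mechanisms can push the estimate in opposite directions, so the sign of the bias cannot be known in advance.

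Baseline-only weights adjust for what baseline predicts. They cannot adjust for events that arise after randomisation.

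**Working it through.** **1. The passages side by side.** The sharpest conflict is one event with two instructions. Protocol 8.11 lists "Treatment at day of infusion with anticholinergic medications (e.g. Physostigmine, Biperiden, Procyclidine") beneath the withdrawal sentence. Protocol 9.8.2 names the same three drugs and keeps those participants in follow-up and in the analysis. The treated haemodynamic reason in 8.11 meets 8.7 in the same way: withdrawal in one place, completion of the remaining visit procedures in the other.

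**2. The plan's own power figure.** Inputs from Protocol 11.2: difference 12, SD 13, two-sided alpha 0.05, 22 per arm. Noncentrality = 12 / (13 × √(2/22)) = 3.06 on 42 degrees of freedom. Exact t power is 84.9% (normal approximation 86.5%), so the stated 85% reproduces. The allowance is 6 of 50 = 12%, all causes. With nobody missing, power is 89.2%.

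**3. Simple bias formula (assumption).** If k of 25 in one arm are missing and their mean change is g points worse than the rest of that arm, the observed arm mean is too favourable by (k/25) × g.

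| k lost | g = 6 | g = 12 | g = 18 |
|---|---|---|---|
| 1 | 0.24 | 0.48 | 0.72 |
| 3 | 0.72 | 1.44 | 2.16 |
| 5 | 1.20 | 2.40 | 3.60 |

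Loss concentrated in placebo biases against scopolamine. Loss concentrated in scopolamine biases in its favour. Equal loss largely cancels.

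**4. Outcome-dependent loss scenario (assumption).** Visit 6 scores are normal with means 24 and 12 (Protocol 11.2) and SD 13. The worst 12% across both arms are removed, either all of them or a random half.

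- Cut-off c solves ½[1 − Φ((c − 24)/13)] + ½[1 − Φ((c − 12)/13)] = 0.12, giving c = 34.9. Above it lie 20.1% of placebo (about 5 of 25) and 3.9% of scopolamine (about 1 of 25).
- Mean of those above the cut-off, μ + 13 × φ(z)/(1 − Φ(z)) with z = (c − μ)/13: 42.16 for placebo and 40.13 for scopolamine.
- All lost: placebo (24 − 0.2009 × 42.16)/0.7991 = 19.43; scopolamine (12 − 0.0391 × 40.13)/0.9609 = 10.86; difference 8.6.
- Half lost: placebo (24 − 0.1005 × 42.16)/0.8995 = 21.97; scopolamine (12 − 0.0195 × 40.13)/0.9805 = 11.44; difference 10.5.

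Power was simulated directly (25 per arm, 40,000 trials, t-test on the participants left): about 71% if all are lost (44 remain) and about 82% if half are lost (about 47 remain).

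**5. Sensitivity.** Across the plan's SD range of 5 to 13, the all-lost estimate runs from 10.0 to 8.6 and the half-lost estimate from 11.1 to 10.5. Adding the planned ANCOVA and baseline weights in a large simulated sample, with an assumed baseline to Visit 6 correlation of 0.5 and SD 13, gives 9.1 and 10.9. The planned method therefore recovers only a small part of the shortfall.

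**The case against.** The best defence is that withdrawn does not mean unobserved here. Section 8.11 itself asks for day 15 and day 29 follow-up, offers a telephone interview and allows one exception only. Section 8.3.6 permits telephone visits for withdrawn participants, and any Visit 6 score obtained is analysed. This stands. A reader might infer that the protocol prescribes dropping the worst outcomes from the primary analysis; the documents do not support that, and no passage discards data from withdrawn participants. What remains is that the withdrawal sentence is mandatory while the follow-up sentence opens as an ideal.

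It is also fair to say that pregnancy, the listed medical conditions, haemodynamic events and anticholinergic use do not in themselves imply a poor HDRS. A reader who treats all seven reasons as deterioration goes too far.

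The mixed model of HDRS over time (Protocol 11.5.2, SAP 13.2) can use scores recorded after randomisation and before withdrawal. That helps, but it is an additional analysis and not the primary one.

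Finally, a reader might put 10.5 into the plan's formula with 22 per arm and SD 13 and obtain 74% power. That mixes scenarios: losing half of the worst 12% removes about 3 of 50, not 6, and removing high scores also shrinks the SD. Simulated directly, the figure is about 82%.

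**Conclusion.** The contradiction is real and should be reconciled before it affects data collection. The loss of Visit 6 HDRS is a risk created by ambiguous wording, not a planned outcome.

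Its size rests on assumptions, because the documents give neither a withdrawal rate nor outcomes for withdrawn participants. With a true difference of 12 and SD 13, losing half of the worst 12% gives about 10.5 and 82% power. Losing all of them gives about 8.6 to 8.7, depending on whether the cut-off is fixed or the six worst scores in each trial are taken, and about 71% power. The second case is an upper bound, since it assigns the whole 12% all-cause allowance to the worst scores and assumes that no follow-up is obtained. If loss falls mainly on scopolamine participants who do badly, the bias runs the other way.

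The 6-participant allowance protects power against a smaller sample. It gives no protection against selective loss, and that bias is the main harm.

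**What to change.** Reconcile 8.11 with 8.7, with 9.8.2 and with its own later text. The reasons for stopping infusions are for the sponsor and need not change for this purpose.

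- In 8.11, replace the clause on withdrawal from the study with a statement that participants who stop infusions for any reason remain in the study for the Visit 6 and Visit 7 assessments, by telephone if needed, unless they withdraw consent for follow-up.
- In the later follow-up sentence of 8.11, delete the opening word Ideally, so that it agrees with the requirement stated after it.
- In SAP 14.4, separate stopping treatment from stopping data collection.

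The cost is a wording amendment and a few extra follow-up interviews. The telephone route already exists, and the right to withdraw consent is untouched.
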